Up to 43 patients will be enrolled with metastatic/recurrent ACC of any site of origin with evidence of disease progression who are not candidates for curative surgical or radiation therapy. An exploratory cohort of 20 patients with non-ACC of major or minor salivary glands will be enrolled concurrently.

**The first 15 ACC patients will be assessed for safety, and ACC accrual will be terminated if ≥ 7 patients are withdrawn after <24 weeks of treatment for any reason other than withdrawal of consent. Otherwise, enrollment will continue for a total of 43 ACC patients. The exploratory cohort of 20 non-ACC MSGT's will follow an independent accrual process to ACC and will also be assessed for safety; if >2 of the first 10 non-ACC patients are withdrawn after <24 weeks of treatment, the non-ACC cohort will be closed to accrual.

[figure not shown]

NU Study Number: NU 16N03
BMS Study Number: CA 209-802

STUDY SUMMARY

Title	Phase II study of nivolumab and ipilimumab for treatment of metastatic/recurrent adenoid cystic carcinoma of all anatomic sites of origin and non-adenoid cystic carcinoma malignant tumors of the salivary gland
Version	October 6, 2022, Amendment 8
Study Design	Simon two-stage single arm multi-center phase II clinical trial
Study Center(s)	Northwestern University
Objectives	
Primary:
 
 (1) To assess median progression-free survival (PFS) as well as PFS at 6 and 12 months in patients with recurrent or metastatic adenoid cystic carcinoma treated with a combination of nivolumab and ipilimumab. 
Secondary:
 
 (1) To assess the efficacy of nivolumab and ipilimumab according to response rate (RR), disease control rate (DCR) or clinical benefit rate (CBR) at 6 and 12 months- defined as sum of CR, PR, and SD, overall survival (OS) and progression free survival (PFS) in the above population using RECIST criteria. (2) To assess the efficacy of nivolumab and ipilimumab according to ORR, DCR, PFS, and OS in the above population using immune-related RECIST (irRECIST) criteria. (3) To assess the safety and tolerability profile of nivolumab and ipilimumab therapy in the above population using CTCAE version 4.03 
Exploratory:
 
 (1) To assess the immune-related biomarkers and their association with treatment response (2) To assess activity of nivolumab and ipilimumab in non-ACC malignant salivary gland tumors (MSGTs) using OS, PFS, CBR, and ORR

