4.4 Treatment with ipilimumab and or nivolumab beyond progression

In the event of an initial assessment of PD (based on RECIST Version 1.1), a subject may continue to receive the assigned study treatment as long as none of the criteria listed below are met.

- a. Confirmed PD: a subsequent scan obtained no sooner than 4 weeks from prior scan is suggestive of PD by RECIST 1.1 (see section 6.6), and the patient has clinical decline. NOTE: If PD is confirmed but the patient continues to have clinical benefit (e.g. improvement of symptoms and is tolerating treatment), the patient can continue treatment beyond PD per clinician's discretion.
- b. Meets any of the other investigational product discontinuation criteria (Section 4.3.2)
- c. Clinical symptoms or signs indicating significant PD, for example the benefit-risk ratio of continuing therapy is no longer justified.
- d. Decline in ECOG performance status.
- e. Threat to vital organs/critical anatomical sites (e.g., spinal cord compression) requiring urgent alternative medical intervention, and continuation of study therapy would prevent institution of such intervention.

If the lesions included in the tumor burden subsequently regress to the extent that the criteria for PD are no longer met, then treatment may continue according to the treatment schedule.

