4.5 Interim Safety Analyses

Enrollment will be paused for a safety analysis after the first 15 evaluable ACC patients have been enrolled and treated. If ≥ 7 patients have been discontinued after <24 weeks of treatment for any reason (including toxicity, progression, intolerance etc.) accrual of ACC patients will be terminated. Otherwise, the study may continue enrollment until a total of up to 43 ACC subjects are treated.

An additional 20 patients with non-ACC MSGT's will be treated as an exploratory cohort. They can be enrolled at any point throughout the study and will not count toward the 15-patient safety analysis. A separate safety analysis will take place to analyze the first 10 non-ACC patients who are enrolled and treated. If >2 patients discontinue treatment prior

NU Study Number: NU 16N03
BMS Study Number: CA 209-802

to 24 weeks (for reasons other than withdrawal of consent), accrual of non-ACC patients will discontinue.

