4.8 Duration of Follow Up

All patients will be followed for adverse events for 30 days after last dose of nivolumab and or ipilimumab (100 days for SAEs), or until the patient starts a new treatment, whichever occurs first. Patients who discontinue treatment for unacceptable adverse event(s) will be followed until resolution or stabilization of the adverse event (i.e. the grade is not changing). If a patient stops treatment due to unacceptable adverse event(s) but has not demonstrated disease progression, then the patient will be followed with imaging studies every 12 weeks until the time of progression radiographically according to RECIST 1.1 criteria. In the event that a radiographic response is detected, then this event will be included as a response in the final analysis, and the time of progression used in calculation of the survival analysis. Patients will be seen in clinic every 4 weeks for the first 12 weeks after treatment discontinuation. Thereafter, patients will be followed for survival (by clinic visit or phone call) every 12 weeks for 2 years from treatment discontinuation or until death, whichever occurs first.

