10.2 Sample Size and Accrual

A Simon two stage optimum Phase II design will be used ⁴⁶. The main outcome is median Progression Free Survival (PFS) as well as PFS at 6 and 12 months. The optimal two-stage design to test the null hypothesis that $P \leq 0.450$ versus the alternative that $P \geq 0.650$ has an expected sample size of 24.70 and a probability of early termination of 0.654. If the drug is actually not effective, there is a 0.048 probability of concluding that it is (the target for this value was 0.050). If the drug is actually effective, there is a 0.196 probability of concluding that it is not (the target for this value was 0.200). After testing the drug on 15 patients in the first stage, ACC accrual will be terminated if 7 or more patients are withdrawn from the study after <24 weeks of treatment for any reason other than withdrawal of consent (this includes toxicity, PD, intolerance etc.) If the trial goes on to the second stage, a total of 43 patients will be studied. If the total number responding (defined as stable disease or better) is less than or equal to 24, the drug is rejected. An exploratory group of 20 patients with MSGTs will be included in the study, in addition to the 43 patients mentioned above. They can be enrolled in any order within the total accrual of 63 patients and will not participate in statistical analysis. A separate safety analysis will take place; if >2 of the first 10 non-ACC patients are withdrawn after <24 weeks of treatment, non-ACC accrual will discontinue.

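### The stage-1 stop at 7 or more of 15 withdrawn is one patient stricter than the Simon design whose properties are quoted; with one outcome at both stages, power is 0.704, not 0.804

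*Combined protocol and SAP*

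**What the plan says.** Section 10.2 states that "A Simon two stage optimum Phase II design will be used", testing a null rate of 0.45 against 0.65. The design "has an expected sample size of 24.70 and a probability of early termination of 0.654", with type I error 0.048 and type II error 0.196, so power 0.804. The first stage has 15 ACC patients and the total is 43.

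The stage-1 rule in the same paragraph is that "ACC accrual will be terminated if 7 or more patients are withdrawn from the study after <24 weeks of treatment", not counting withdrawals of consent. The final rule is: "If the total number responding (defined as stable disease or better) is less than or equal to 24, the drug is rejected".

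The Study Summary (Statistical Methodology) repeats all of this. The Study Schema has the same threshold: "ACC accrual will be terminated if ≥ 7 patients are withdrawn after <24 weeks of treatment", again leaving out consent withdrawals. Section 4.5 also uses 7 or more, but counts discontinuation "for any reason (including toxicity, progression, intolerance etc.) accrual of ACC patients will be terminated". It gives no consent exception for ACC patients, although it gives one for the non-ACC cohort.

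**The concern.** A Simon boundary is a number of successes. The plan writes its stage-1 boundary as a number of early withdrawals. With 15 patients, 7 or more failures is the same event as 8 or fewer successes, whereas the quoted figures appear to belong to 7 or fewer successes. If so, the go/no-go rule for the primary cohort and its stated properties cannot both be right, and the rule that would be applied stops an effective regimen more often than the plan says.

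Two related inconsistencies affect the same figures:

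- **Different outcomes at the two stages.** Stage 1 counts withdrawal before 24 weeks; the final test counts stable disease or better. These can diverge. After a first progression, Section 4.4 says "a subject may continue to receive the assigned study treatment as long as none of the criteria listed below are met". For patients who stop because of toxicity without progression, Section 4.8 says "In the event that a radiographic response is detected, then this event will be included as a response in the final analysis".
- **Consent withdrawals.** These are excluded from the ACC count in the Study Schema, the Study Summary and Section 10.2, but not in Section 4.5.

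**Working it through.** **Inputs** (Section 10.2): p0 = 0.45, p1 = 0.65; n1 = 15, n = 43, so 28 patients in stage 2; final cutoff r = 24, so at least 25 successes are needed.

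**Formulas.** Let X1 ~ Bin(15, p) and X2 ~ Bin(28, p), and let r1 be the largest number of stage-1 successes at which the trial stops.

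- PET (probability of early termination) = P(X1 ≤ r1)
- EN (expected sample size) = 15 + 28 × (1 − PET)
- P(declare effective) = Σ over x > r1 of P(X1 = x) × P(X2 ≥ 25 − x)

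The last line gives type I error at p = 0.45 and power at p = 0.65. It assumes one binary success counted the same way at both stages, as the quoted Simon figures do.

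**Reproducing the plan, r1 = 7** (stop at 8 or more failures). PET at 0.45 is 0.6535 and EN = 15 + 28 × 0.3465 = 24.70. Type I error is 0.0481, power 0.8035 and type II error 0.1965. All four stated figures are recovered. With n1 = 15 and n = 43 no other r1 gives this PET or EN. In a search over maximum sizes from 20 to 60, this design also had the lowest EN with type I error at most 0.05 and power at least 0.80.

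**The written rule, r1 = 8** (stop at 7 or more failures). The outcome of exactly 8 successes moves from continuing to stopping:

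- At 0.45: PET = 0.65350 + C(15,8) × 0.45^8 × 0.55^7 = 0.65350 + 0.16474 = 0.8182, and EN = 15 + 28 × 0.1818 = 20.09.
- At 0.65: P(stop) = 0.11323 + C(15,8) × 0.65^8 × 0.35^7 = 0.11323 + 0.13193 = 0.2452.

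| | Stated | Stop at 8+ failures | Stop at 7+ failures (as written) |
|---|---|---|---|
| PET at 0.45 | 0.654 | 0.6535 | 0.8182 |
| EN at 0.45 | 24.70 | 24.70 | 20.09 |
| Type I error | 0.048 | 0.0481 | 0.0367 |
| Type II error | 0.196 | 0.1965 | 0.2958 |
| Power | 0.804 | 0.8035 | 0.7042 |
| P(stop at stage 1) at 0.65 | not stated | 0.1132 | 0.2452 |

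**Can the final cutoff recover the power?** No. Since P(stop) at 0.65 is 0.245, power cannot exceed 1 − 0.245 = 0.755 at any cutoff. Lowering the cutoff to 23 gives power 0.731 and already takes type I error to 0.0575.

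**Sensitivity to consent withdrawals** (one or two among the first 15, an assumption).

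- Not counted, rule as written: P(stop) at 0.65 is P(Bin(15 − k, 0.35) ≥ 7) = 0.184 for k = 1 and 0.129 for k = 2; at 0.45 it is 0.741 and 0.644. Power is 0.72 to 0.75 and 0.71 to 0.79. The low end treats these patients as non-successes at the end; the high end gives each a 0.65 chance of success.
- Counted, as Section 4.5 literally reads: P(stop) at 0.65 is 0.359 and 0.499.

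**Sensitivity to differing outcomes** (final success fixed, one outcome nested in the other, an assumption). If the chance of staying on treatment to 24 weeks is 0.60, 0.65 or 0.70, P(stop) under the written rule is 0.390, 0.245 or 0.131, against 0.213, 0.113 or 0.050 with 8 or more. With final success at 0.65, power under the written rule is 0.58, 0.70 or 0.79; it reaches 0.83 if retention is 0.75.

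These figures concern the 15/43 rule only. The separate 12-participant stop in Sections 8.1.11 and 8.2.11 is not modelled.

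**The case against.** **It may be a deliberate safety stop.** Section 4.5 is an interim safety analysis, and the Study Schema says the first 15 are assessed for safety, so a stricter count could be intended. But Section 10.2 places the count in the first stage of the Simon design, directly after the design properties, includes progression in it, and gives no other stage-1 futility boundary. Even a deliberate safety stop changes early termination, expected size and both error rates, so the quoted figures would still not describe the trial. What stands is that the threshold need not be the part that is changed.

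**0.704 is conditional.** It requires that remaining on treatment to 24 weeks and stable disease or better are the same outcome, which the plan does not ensure. The sensitivity range shows that power could be well below 0.70 or above 0.80. This stands, but it does not rescue the plan: if the outcomes differ, the quoted Simon figures do not apply either.

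**The type I statement is conditional too.** With final success at 0.45 and 24-week retention of 0.60 to 0.70, type I error under the written rule is about 0.053 to 0.057. It cannot exceed 0.0576, the value for a single-stage test at 25 of 43. Any inflation is therefore small.

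**The 8-or-more boundary is not exact if consent withdrawals stay excluded.** With one or two uncounted, its early termination probability at 0.45 is 0.546 or 0.427. This also stands, and is a reason to state the boundary as a number of successes out of 15.

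**Conclusion.** The concern holds. The threshold of 7 or more is the same in all four places, and none supplies a boundary that fits the quoted figures. Assuming one common success at both stages and no consent withdrawals, power is 0.704 instead of 0.804, about 10 points lower. The chance of stopping an effective regimen at stage 1 is about twice that of the quoted design (0.245 against 0.113). Under the same assumptions type I error falls to 0.037, so a positive result is no less reliable; the harm is lost power and mis-stated design properties. A likely cause is that a bound of 7 or fewer responding was rewritten as 7 or more withdrawn, but the documents do not say so.

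**What to change.** Reconcile the threshold with the quoted figures in the Study Schema, the Study Summary, Section 4.5 and Section 10.2. There are two equally acceptable ways:

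- **(a)** If the rule is meant as the Simon futility boundary, use the one that generates the figures: stop at 7 or fewer successes of 15 (8 or more failures). Cost: a null regimen is stopped at stage 1 less often (0.654 rather than 0.818), expected size under the null rises from 20.1 to 24.7, and a stop also presented as a safety check tolerates one more early withdrawal.
- **(b)** If 7 or more is deliberate, or stage 1 has already been run with it, keep it and restate early termination 0.818, expected size 20.1, type I error 0.037 and power 0.704. Cost: the stated power becomes about 70%.

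In either case, the same edit should define one success outcome for both stages, since otherwise neither set of figures holds, and give one statement of how consent withdrawals among the first 15 ACC patients are handled. If those patients stay excluded from the count, the properties should be recomputed for that rule. The work is text edits in four places, and the maximum of 43 ACC patients does not change.

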discretion) with contrast unless strictly contraindicated; the same modality used at baseline should be used throughout. Brain MRI should be performed at baseline if clinically indicated, \leq 6 weeks prior to registration. Tumor assessment (incorporating both RECIST and clinical criteria) should be done Day 1 of every cycle, i.e. every 12 weeks (\pm 7 days) starting with Cycle 2, until progression or treatment discontinuation whichever occurs first.

⁴ Earlier scans may be performed at the discretion of the treating physician.

⁵ If PD is confirmed at any time, see section **4.4** on how to determine whether patient can be considered for further treatment. If patient continues, scans should be obtained every 8 weeks until PD is confirmed by 2 consecutive scans.

⁶ CBC with differential will be collected within 14 days of registration and at each treatment visit, pre-treatment. It will include WBC, ANC, ALC, Platelets, and Hemoglobin.

⁷ Chemistry panel will be collected within 14 days of registration and at each treatment visit, pre-treatment. It will include glucose, calcium, albumin, ALT, AST, sodium, potassium, total bilirubin, alk phos, and creatinine.

⁸ Amylase and lipase will be assessed at screening and every 6 weeks (Day 1 and 43 of each cycle) pre-treatment.

⁹ TSH will be tested at screening and every 6 weeks (Day 1 and 43 of each cycle), pre-treatment. If TSH is abnormal, free T4 should be tested

¹⁰ Serum or urine test for females of child-bearing potential (FOCBP) \leq 14 days prior to registration. FOCBP are also required to have a negative pregnancy test within 24 hours of starting nivolumab.

¹¹ Nivolumab will be administered in combination with ipilimumab as follows:

First 8 doses (Cycle 1, C2D1, & C2D15): 240mg IV q2weeks

Starting with C2D29: 480mg IV q4weeks until disease progression, intolerable toxicity or withdrawal of consent.

¹² Ipilimumab will be administered IV at 1mg/kg over 90 minutes every six weeks in combination with nivolumab. Dosing will be based on weight at baseline unless there is a change \geq 10%. Nivolumab will be given before ipilimumab.

¹³ A correlative blood sample (3x 8ML heparin tubes) will be drawn at baseline (C1D1, pre-dose), at the first scheduled study visit after response is confirmed (PR or CR), and at the end of treatment visit. Please see separate lab manual for details.

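### The stage-1 count uses withdrawal before 24 weeks of treatment, a cut that falls on the second scan, so progression found by then need not count as failure and the stopping probability is not determined

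*Combined protocol and SAP*

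**What the plan says.** In the combined protocol and SAP, Section 10.2 sets out a Simon two-stage design. It states that "The main outcome is median Progression Free Survival (PFS) as well as PFS at 6 and 12 months", and it tests a null P of 0.45 against 0.65. It says the design "has an expected sample size of 24.70 and a probability of early termination of 0.654", with type I error 0.048 and type II error 0.196.

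The stage-1 decision does not count progression. It closes ACC accrual if 7 or more of 15 patients are "withdrawn from the study after <24 weeks of treatment for any reason other than withdrawal of consent", and it names toxicity, progression and intolerance as counting reasons. The Study Schema, Study Summary and Section 4.5 use the same 24-week cut. At the end, the drug is rejected if 24 or fewer of 43 patients have stable disease or a response, with no timepoint given.

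Three other places bear on the cut:

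- Table 1 in Section 4.2 gives a cycle of 84 days.
- Section 5.0, footnote 3, says tumour assessment "should be done Day 1 of every cycle, i.e. every 12 weeks", with a 7-day window either side, starting with Cycle 2. Footnote 4 allows earlier scans.
- Section 4.4 says that after a first assessment of progression "a subject may continue to receive the assigned study treatment as long as none of the criteria listed below are met". Footnote 15 of Section 5.0 runs treatment to confirmed progression, and footnote 5 sets 8-weekly scans until progression is confirmed.

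**The concern.** A Simon design needs one yes/no outcome with one success probability. Here the stage-1 count (withdrawal before 24 weeks), the main outcome (PFS at 6 and 12 months) and the final count (stable disease or better, undated) are three different things.

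The stage-1 cut falls on the nominal date of the scan that largely decides 6-month PFS, and nothing says how progression found at that scan is classified. Continuation after first progression adds a second route by which a progressor is not counted.

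Two teams could apply Section 10.2 to identical data and reach opposite decisions on closing accrual. What is at stake is mainly the futility stop: how often an ineffective regimen is stopped at 15 patients, and how many more are treated if it is not.

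**Working it through.** **Dates** (84-day cycles, Table 1 doses, Section 5.0 scan window).

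- C3D1 is day 2 × 84 + 1 = 169, which is 168 days or 24.0 weeks after C1D1. The scan window is days 162 to 176, or 23.0 to 25.0 weeks elapsed.
- The last nivolumab dose before C3D1 is C2D57, day 84 + 57 = 141, or 20.0 weeks elapsed.
- The last ipilimumab dose before C3D1 is C2D43, day 84 + 43 = 127, or 18.0 weeks elapsed.

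**Classification of progression found at the second scan.**

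- Treatment stops at the scan and time runs to last dose (18 to 20 weeks): counted.
- Treatment stops at an on-time or late scan and time runs to that date (24.0 weeks or more): not counted.
- The patient continues under Section 4.4 past week 24: not counted on either measure. A patient with progression at week 12 who continues that long also escapes.

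**The plan's own figures.** With X ~ Bin(15, 0.45) successes, P(X ≤ 7) = 0.6535. Expected N = 15 + 28 × (1 − 0.6535) = 24.70. With final rejection of the drug at 24 or fewer of 43, type I error is 0.0481 and power at 0.65 is 0.8035. All four stated figures reproduce, but they belong to a stop at 7 or fewer successes, that is 8 or more failures. The written stop at 7 or more failures (8 or fewer successes), with every week-24 failure counted, gives early termination 0.818, expected N 20.1, type I error 0.037 and power 0.704.

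**Effect of not counting second-scan progressions.** Assumptions: P is the week-24 progression-free rate, failure is progression or death only, and the hazard is constant. The documents give no split of failures between the two scans. Under the null, S(24) = 0.45 and S(12) = √0.45 = 0.671. If a share c of second-scan progressions is counted, the counted failure probability is

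q = (1 − 0.671) + c × (0.671 − 0.45).

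The stopping probability is P(Bin(15, q) ≥ 7) for the written rule, or ≥ 8 for the boundary behind the stated figures. Expected N is 15 + 28 × (1 − stopping probability).

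| Share counted | q | Stop, ≥7 (written) | Stop, ≥8 | Expected N, ≥7 | Expected N, ≥8 |
|---|---|---|---|---|---|
| All | 0.550 | 0.818 | 0.654 | 20.1 | 24.7 |
| Half | 0.440 | 0.515 | 0.316 | 28.6 | 34.1 |
| None | 0.329 | 0.193 | 0.083 | 37.6 | 40.7 |

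**Sensitivity to the hazard.** With none counted under the written rule, Weibull shapes 0.5, 1 and 2 give stopping probabilities of 0.489, 0.193 and 0.010.

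**Type I error.** There are two cases.

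- The final 24/43 count uses true outcomes. Each stage-1 patient is a counted failure (q), a missed failure (0.55 − q) or a success (0.45), and the drug is accepted with 25 or more true successes of 43. Written rule: 0.050 (half counted) and 0.056 (none). Eight-failure boundary: 0.055 and 0.057. Removing the interim altogether gives P(Bin(43, 0.45) ≥ 25) = 0.058, which is the ceiling.
- Missed stage-1 progressors are carried as successes into the final count (stage-1 rate 1 − q, stage-2 rate 0.45). Written rule: 0.12 and 0.27. Eight-failure boundary: 0.14 and 0.28.

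**The case against.** A reader might infer that progression at the second scan is excluded, that the futility stop therefore loses most of its stated 0.654, and that the false-positive rate rises as high as 0.28. The documents do not support that reading.

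- No section excludes second-scan progression. A patient taken off at C3D1 before dosing had the last doses at weeks 18 and 20 and, measured to last dose, is a failure.
- Scans on days 162 to 168, and the earlier scans that footnote 4 allows, can bring progression to light before 24 weeks.
- Toxicity and intolerance exits count as failures. The model leaves them out, and they push the stopping probability up.
- Loss of most of the stop needs nearly all second-scan progressions to be missed under an assumed hazard. With half counted, the written rule still stops with probability 0.52.
- The 0.28 requires missed progressors to remain successes in the final count, which the plan does not say. If the final count uses true outcomes, type I error barely moves.

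All of this stands. It does not remove the point. The last-dose reading is only one of those the text allows, and it does not help for a patient who continues past progression beyond week 24. The mismatch between counting withdrawals and measuring PFS remains on every reading.

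**Conclusion.** The concern holds as an indeterminate and mismatched stage-1 outcome. Progression at or before the second scan need not be counted as a stage-1 failure, and the plan does not say when it is.

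Under the stated assumptions, the written rule stops a null regimen with probability between 0.19 and 0.82, depending only on how second-scan progression is classified. The stated 0.654 matches neither end. Expected N ranges from 20 to about 38 under the written rule, and reaches about 41 at the eight-failure boundary.

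These are not hard bounds. Toxicity exits raise the stopping probability, and continuation after progression at week 12 or a later-rising hazard lowers it. P itself is not defined in the plan; equating it with the week-24 rate is an assumption.

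The main harm is a weakened futility stop and more patients treated with an ineffective regimen. Type I error stays at or below 0.058 if the final count uses true outcomes.

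**What to change.** In the Study Schema, Study Summary, Section 4.5 and Section 10.2:

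1. Define one binary efficacy outcome: alive and progression-free by RECIST 1.1 through the C3D1 assessment (scan window to day 176), whatever the date treatment stops. Use it for both the stage-1 and the 24/43 decisions, and state that P is this rate.
2. State how toxicity and intolerance exits enter. Either keep them as failures in both counts, or keep the existing withdrawal count as a separate safety rule. They should not be deleted, because Section 4.5 presents this look as a safety analysis.
3. Reconcile the stage-1 cut-off with the stated figures, or restate them for the cut-off kept. Seven or more failures gives early termination 0.818, expected N 20.1, type I error 0.037 and power 0.704. Redefining the outcome alone would leave the stated 0.654 and 0.804 power wrong for the written rule.
4. Reconcile Sections 4.5 and 10.2 on withdrawal of consent, which only Section 10.2 exempts for the ACC count.

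The rules on treatment after progression need not change, since the outcome no longer depends on when treatment stops. The cost is protocol wording and an interim read that waits up to about one more week for the scan window to close. No scans or visits are added.
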